5.1.5 ANGIOGRAM ACQUISITION GUIDELINES

Angiographic imaging will be performed per standard of care; however, the following items should be included on the fluoroscopy during the catheterization for all non-culprit arteries:

- All catheters used throughout the procedure should be clearly visualized in the diagnostic cines with a straight (non-tapered) portion of the unfilled catheter for off-line image calibration. The catheter and segment of interest should be centered in the image. At least 1 cardiac cycle, before contrast injection, should be recorded for calibration of empty catheter tip.
- Qualitative and quantitative analysis will be performed using at least 2 (two) orthogonal angiographic views of the lesion.
- Intracoronary NTG is not required. However, if given during the procedure usage will be recorded on the angiographic technician's worksheet.
- If a PCI is pursued during the procedure this will be noted on the angiographic technician's worksheet.
- All catheter sizes used during the catheterization should be recorded as specified above and listed on the angiographic technician's worksheet.
- Images of the TVC™ IVUS-NIRS catheter distal and proximal placements should be recorded by fluoroscopy and recorded on the angiographic technician's worksheet for each run performed.

5.1.6 TVC™ CORONARY IVUS-NIRS IMAGING GUIDELINES

All IVUS-NIRS imaging will be performed, either in the culprit or non-culprit arteries utilizing the automatic, motorized pullback device. The IVUS-NIRS catheter should be positioned as distal as clinically feasible within each vessel. The pull back should continue as proximal as clinically feasible. Fluoroscopy capture of the IVUS-NIRS catheter marker positioning should be recorded on cine run prior to initiation of the automatic, motorized pull back; this should then be repeated upon completion of the pull back. The pull back start and stop time for both Suspected Index Culprit Lesion and Non-Culprit Arteries will be recorded within the case report form.

Within each native epicardial artery the maximum suitable distance of artery will be imaged. All study artery/vessel imaging will occur using the automatic pullback transducer at a rate of 0.5mm/second.

Suspected Index Culprit Lesion or Lesions -- IVUS-NIRS Assessment:

For a native artery deemed by the physician to require clinically-indicated IVUS interrogation, the TVC console will image and record the IVUS and NIRS findings in an unblinded fashion (meaning, both the IVUS and NIRS images and details as provided on the commercially available TVC system will be available to the clinical site for diagnosis and treatment of the artery). The TVC system will display the images and details for all pull-backs performed within the Suspected Index Culprit Artery throughout the imaging and, if needed, for treatment of the Index Culprit Artery. The denotation of "suspected culprit" and "culprit" will be recorded on the case report form.

Once the clinical team determines that all of the clinically-indicated IVUS has been completed, the clinical team will switch the TVC System to the NIRS-blinded mode, as specified in the Manual of Operations for the LRP Study.

Index Non-Culprit Artery or Arteries -- IVUS-NIRS Assessment:

For a artery that does not require clinically-indicated IVUS imaging, the TVC console will image and record the NIRS findings in a blinded fashion, only displaying the IVUS findings to the clinical site (meaning, only the IVUS images and details as provided on the commercially available TVC system will be available to the physician. The denotation of 'non-culprit' will be recorded on the case report form.

The processes for establishing the TVC system to blind the NIRS findings on the console are located in the Manual of Operations for the LRP Study.

Study Segment(s):

The portion of the coronary artery or arteries to be studied will meet all of the following criteria:

- The portion of the coronary artery does not contain a flow-limiting stenosis, defined as > 50% diameter stenosis by visual angiographic estimate;
- The portion of the coronary artery has not undergone PCI in the past, and PCI is not performed at the index event or planned in a staged procedure. The length of artery excluded from the study because of PCI includes a 5mm border on either side of the intervened segment;

For the off-line Core Laboratory NIRS analysis will include the following definitions for the vulnerable plaque-based primary endpoint evaluation.

For each coronary artery with available IVUS-NIRS imaging, the proximal segment will be defined as the first 30mm of the proximal chemogram obtained in that vessel, the mid segment as the next 30mm, and the distal segment as the remaining chemogram up to a 30mm segment. If the total chemogram of a vessel exceeds 90 mm, the segment beyond 90 mm will be defined as the far distal segment. This anatomic specificity will be important in the Vulnerable Plaque analysis, as described below.

Additionally, the coronary artery analysis will be broken into 10mm segments in a similar hierarchal fashion as mentioned above for the 30mm segment analysis. This 10mm segmentation in a hierarchal fashion within each epicardial vessel will be analyzed as a tertiary endpoint.

5.2 STUDY WITHDRAWAL

The only acceptable reason for withdrawal from the study is the subject's (or legal guardian's) withdrawal of consent. All reasons for withdrawal (if given) will be recorded in the source documentation.

5.3 PROTOCOL VIOLATIONS

All deviations from clinical protocol requirements, including ICH/GCP guidelines referred to in this protocol, will be considered protocol violations. A 'serious violation' is one that may affect the scientific soundness of the protocol or one that would affect the rights, safety, or welfare of the subjects.

Subject level deviations are those that occur in direct association with a specific study subject. These include, but are not limited to, deviations from Informed Consent procedures, inclusion/exclusion criteria, required clinical assessments.

6 STATISTICAL CONSIDERATIONS

6.1 STATISTICAL ANALYSIS

The Lipid-rich Plaque Outcomes Study is a global, multicenter prospective cohort study of patients who have undergone IVUS-NIRS coronary imaging to determine the extent and size of non-flow-limiting LRP's in their

coronary arteries. The objective of the study is to determine whether the presence of one or more LRPs is predictive of subsequent coronary events. A patient-level (Vulnerable Patient) and a plaque-level analysis (Vulnerable Plaque) will be conducted.

Primary Hypotheses:

The study will test two primary hypotheses, stated here in terms of the null hypothesis:

H1: Vulnerable Patient Hypothesis – During 24-month follow-up after IVUS-NIRS imaging, there will be no association between the baseline value of max 4mm LCBI (over all coronary artery segments included in the analysis) and the incidence of non-culprit NC-MACE events. (This hypothesis will be tested with a time-to-event analysis as described below).

H2: Vulnerable Plaque Hypothesis – During 24-month follow-up, there will be no association between the max 4mm LCBI of the proximal, mid, or distal segment of a coronary artery and the incidence of a culprit lesion in that segment leading to a NC-MACE event.

Additional Objectives:

As noted above, the study will also investigate the prognostic value of multiple novel NIRS measures and conventional IVUS measures that can be evaluated in multiple ways.

Statistical Methods:

To test Hypothesis 1 (the Vulnerable Patient Hypothesis), we will first fit a univariate proportional hazards regression model in which max 4mm LCBI is the only independent variable and NC-MACE is the outcome. The null hypothesis will be tested by the Wald test that the regression coefficient in a proportional hazards regression model is significantly different from 0. This analysis will determine whether max 4mm LCBI is a risk factor for NC-MACE. In supportive analyses, we will assess the validity of the proportional hazards assumption. We will also investigate the predictive value of the binary variables defined by varying cut-points of max 4mm LCBI. The analyses using these cut-points will be used to calculate an ROC curve characterizing the prognostic value of presence of a lipid-rich plaque. Weighted estimation will be required to estimate the ROC curve because of the underrepresentation of 3,000 individuals (absence of follow-up data) with no segments with max 4mm LCBI \geq 250 in the follow-up cohort.

In multivariate analysis, we will assess the incremental prognostic value of lipid-rich plaques by fitting proportional hazards regression models that include the max 4mm LCBI value and other identified prognostic variables. To identify the variables to be included in the multivariate model, we will perform a step-up regression blinded to the NIRS and IVUS data to identify the prognostic factors other than NIRS or IVUS data associated with the NC-MACE outcome. When that model has been selected, max 4mm LCBI will be added to the model to assess its incremental prognostic value. This will be the definitive test of Hypothesis 1. Results from these analyses will be used to estimate the net reclassification improvement, a measure of the incremental prognostic value of a new prognostic variable. Weighted estimation will also be required to calculate the NRI. Other covariates to be considered as possible prognostic factors in the NRI analysis include but are not limited to age (10 year units), hypertension, diabetes (any), current smoking (at the time of NIRS evaluation), prior history of coronary disease, history of cardiovascular disease, BMI, index catheterization presentation status (ACS, unstable angina, stable angina, and positive EST), total cholesterol level, use of statin therapy at discharge (as well as prior to index catheterization), requirement for at least 1 lesion treatment at the time of index catheterization), ADP antagonist at discharge, plasma lipid levels at baseline and during follow-up if available and history of renal insufficiency.

In a secondary statistical analysis, we will investigate whether the location of a large LRP within a blinded or non-blinded NIRS recording modifies its association with subsequent NC-MACE events.

To test Hypothesis 2 (the Vulnerable Plaque Hypothesis), we will treat the individual coronary artery segments as separate units of observation, with appropriate adjustment for clustering of segments within patients. A study participant will typically provide results for up to 9 segments. To test this hypothesis, we will fit a proportional hazards regression model with max 4mm LCBI in the coronary artery segment as the measure of exposure and NC-MACE during 24 months caused by a new culprit lesion in that segment as the outcome. All models will include a categorical variable representing the type of coronary artery segment. To identify other characteristics of the coronary artery that should be included in this analysis, we will perform an initial analysis blinded to the value of max 4mm LCBI to determine whether segment type, segment length, or other characteristics of individual segments are risk factors for NC-MACE. Identified segment characteristics will be included in the model used to test the primary hypothesis. All analyses of coronary artery segments will use generalized estimating equations with robust variances to account for clustering of segments within patients.

As in the vulnerable patient analysis, we will investigate the predictive value of the binary variables defined by varying cut-points of max 4mm LCBI. The analyses using various cut-points will be used to calculate an ROC curve characterizing the prognostic value of presence of a lipid-rich plaque in a coronary artery segment. Weighted estimation will be required to estimate the ROC curve because of the exclusion from follow-up of 3,000 of the 9,000 enrolled patients with no segments with max 4mm LCBI \geq 250 in the follow-up cohort and analyses will account for clustering of segments within patients.

Results from the multivariate analyses will be used to estimate the net reclassification improvement obtained by considering max 4mm LCBI of individual segments as a risk factor. Weighted estimation will again be required to calculate the NRI. The covariates considered in the vulnerable patient analysis will again be considered in the vulnerable plaque analysis.

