6.2 SAMPLE SIZE CONSIDERATIONS

A total of 9,000 patients will be enrolled with multi-vessel scans. It is expected based on the PROSPECT Study that at least 720 patients (8%) will experience a NC-MACE event. We expect to find approximately 3,000 patients with large LRP (max 4mm LCBI \geq 250). All 3,000 of these patients will be followed with phone calls for 2 years to identify those who have an event. We expect to observe at least 300 events in this group. From the 6,000 with no or small LRP, a random sample of 3,000 patients will also be followed to determine their event rate, and to examine with IVUS and angiograms those in whom events occur. Of the approximately 2,700 patients with large LRP who do not have an event, a 300 person sample will be selected for IVUS and angiographic analysis to investigate characteristics of the yellow spots that did not lead to events.

Vulnerable Patient Analysis

For hypothesis 1, we will test the hypothesis that there will be no association between the baseline value of max 4mm LCBI (over the entire area scanned) and the incidence of NC-MACE.

In PROSPECT registry results, the 24-month cumulative incidence of NC-MACE in patients was approximately 10%. Subsequent STEMI literature indicates that patients with large LRP will have a higher rate than that observed in PROSPECT.

For the power calculations below, we assumed 6,000 evaluable patients, an event rate between 4 and 8% in the overall LRP study, and a two-sided alpha of 0.05 with a standard deviation of 100 for max 4mm LCBI. Table 2

provides values for the power of the study to detect the following effect sizes: hazard ratio of 1.18, 1.20, and 1.22 per 100 unit increase in max 4mm LCBI (calculated in PASS 12). These results demonstrate that the study will have 80% power to detect a minimal effect size of 1.18 per 100 unit increase in the max 4mm LCBI with 6,000 patients and an overall cumulative incidence of 5% at 24 months. As described in section 5.3, interim analyses will be performed at 6 month intervals.

Table 2: Hypothesis 1: Power Calculation for Vulnerable Patient Hypothesis

2 Year cumulative incidence overall, patient level	Relative Risk per 100 unit increase in max 4mm LCBI		
	1.18	1.20	1.22
8%	0.95	0.98	0.99
7%	0.92	0.96	0.98
6%	0.88	0.93	0.97
5%	0.82	0.88	0.93
4%	0.73	0.81	0.87

Vulnerable Plaque Analysis

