6.3 INTERIM ANALYSIS PLAN

As is evident from the power calculations provided in Section 5.2, for both the patient and segment level analysis, the LRP Study will have excellent power to detect relatively small increases in risk due to the presence of LRP.

The PROSPECT Study, with 700 patients, detected a hazard ratio of 5 for the presence of plaque burden > 70%. If the hazard ratio for increased LCBI reaches or exceeds 5, the LRP Study will provide definitive evidence that max 4mm LCBI predicts NC-MACE well before 6,000 patients have completed two-year follow-up. To provide an

opportunity for an early decision if this should occur, the LRP Outcomes Study will employ an interim analysis plan as described below.

When criteria for demonstrating an association between max 4mm LCBI and risk of NC-MACE have been met, the LRP Study will transition to a treatment study. This treatment study will include a control arm in which more detailed questions regarding the prognostic value of LCBI in various subgroups can be addressed in great detail.

The transition to a treatment study will require submission of a new protocol to the IRBs of the participating centers.

The interim analysis plan for the LRP Outcomes Study will be based on the Pocock spending function for repeated significance testing. This spending function will provide a greater opportunity for early stopping if strong associations emerge than would the O'Brien-Fleming or Haybittle-Peto spending functions. Specifically, review of accumulated data by the Data and Safety Monitoring Committee (DSMB) will occur on December 1, 2014 and at 6 month intervals thereafter until December 1, 2016. The DSMB will review the accumulated data to determine whether, in the multivariate analyses described in Section 5.1, both the vulnerable patient and the vulnerable plaque null hypotheses are statistically significant at the level required by the adjustment for repeated testing provided by the Pocock procedure. If those conditions are met, the DSMB may recommend termination of the study. If the study continues to the planned completion of two-year follow-up of all patients enrolled in the follow-up study, the two null hypotheses will be tested at the same significance level as that employed in the interim analyses. Additional information regarding the interim analysis plan will be provided in the Statistical Analysis Plan (SAP).

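### The definitive test of Hypothesis 1 rests on outcome-driven step-up covariate selection with no entry rule or closed list, so weak confounders can be missed and the LCBI test can reject too often

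*Combined protocol and SAP*

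**What the plan says.** Section 6.1 first fits a univariate Cox model with max 4mm LCBI alone. For the multivariate model it then says "we will perform a step-up regression blinded to the NIRS and IVUS data to identify the prognostic factors". The outcome used for this selection is NC-MACE itself. LCBI is added to the selected model, and "This will be the definitive test of Hypothesis 1".

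No entry level is given and no covariate is forced in. The named candidates come to about 16 terms. The list is expressly not exhaustive, is introduced for the net reclassification analysis, and includes plasma lipids during follow-up, which are post-baseline.

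Section 6.3 carries this model into the stopping rule: "The DSMB will review the accumulated data to determine whether, in the multivariate analyses described in Section 5.1" both primary null hypotheses reach the Pocock level. The cross-reference evidently means 6.1. There are five review dates, from December 2014 to December 2016, and a final test at the same level. The section does not say whether the covariates are selected once or again at each date, and it leaves further interim detail to the SAP.

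For Hypothesis 2, Section 6.1 already puts segment type in every model. It screens other segment characteristics against the outcome, without LCBI: "Identified segment characteristics will be included in the model used to test the primary hypothesis".

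**The concern.** The study wants to show that LCBI adds to known clinical risk. That claim is only as good as the clinical model to which LCBI is added. Step-up selection keeps a factor if it reaches significance in this sample. A real but modest risk factor that is also related to LCBI will often fail to enter, and part of its effect is then credited to LCBI. Because the entry level and the candidate list are open, the model for a primary hypothesis is not defined until outcome data have been seen. A positive result on both hypotheses is also what moves the programme to a treatment study.

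**Working it through.** **1. The plan's own figure.** Section 6.2 gives "we assumed 6,000 evaluable patients, an event rate between 4 and 8% in the overall LRP study", "a two-sided alpha of 0.05 with a standard deviation of 100 for max 4mm LCBI", and "hazard ratio of 1.18, 1.20, and 1.22 per 100 unit increase in max 4mm LCBI". For a continuous covariate in a Cox model,

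power = Φ(√(D(1−R²)) × SD × ln HR per unit − 1.960),

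where D is the number of events and R² is the share of LCBI variance explained by the other covariates. With D = 6,000 × 0.05 = 300, R² = 0 and HR 1.18 per 100 units: 17.32 × 0.1655 − 1.960 = 0.907, and Φ = 0.818. Table 2 shows 0.82. All 15 cells agree within 0.01. So the statement that "the study will have 80% power to detect a minimal effect size of 1.18 per 100 unit increase" is an unadjusted calculation, although the definitive test is adjusted.

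**2. How often a real factor is missed.** For a standardised factor and entry at p<0.05 (assumed), the chance of entry is about Φ(ln HR × √D − 1.960).
- HR 1.11 per SD (ln HR 0.10), 300 events: 1.732 − 1.960 = −0.228, entry 41%, missed 59%. At 32 events it is missed 91% of the time.
- HR 1.28 per SD (ln HR 0.25), 300 events: 4.330 − 1.960 = 2.370, entry 99%, missed 1%. At 32 events it is missed 71% of the time.

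**3. Effect on the LCBI test.** With no adjustment, k independent confounders with correlation ρ and log hazard ratio g shift the LCBI statistic by kρg√D. For k = 4, ρ = 0.2, g = 0.10: 4 × 0.2 × 0.10 × 17.32 = 1.386, and Φ(1.386 − 1.960) = 0.283. Simulation also gives 28.3% unadjusted. Step-up brings this to 7.9% and the forced model to 5.1%. Selection therefore removes most of the confounding, but not all.

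The table shows the final test alone at two-sided 5%, with 16 independent candidates, entry at p<0.05, no true conditional LCBI effect and 300 events. Figures in brackets are a patient-level check (6,000 patients, logistic stand-in for Cox).

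| Assumed confounders, all in one direction | Type I error with step-up |
|---|---|
| None | 5.1% (4.8%) |
| 4, correlation 0.1, HR 1.11 | 5.7% |
| 4, correlation 0.2, HR 1.11 | 7.9% (7.7%) |
| 4, correlation 0.2, HR 1.16 | 6.3% |
| 4, correlation 0.2, HR 1.28 | 5.1% (4.9%) |
| 6, correlation 0.2, HR 1.13 | 10.7% |
| 8, correlation 0.1, HR 1.10 | 8.2% |
| 12, correlation 0.1, HR 1.10 | 12.4% |
| 6, correlation 0.3, HR 1.11 (extreme) | 23.9% |

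With all 16 covariates forced in, the error is 5.1% in the simulation and 4.7% to 4.8% at patient level.

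**4. Sensitivity.**
- *Events.* Section 6.2 also expects 720 events, 300 of them with a large LRP. Half of the other 420 would be followed, so 300 + 210 = 510. The 8- and 12-predictor cases then give 6.9% and 9.9%.
- *Entry level* (4 confounders, correlation 0.2, HR 1.13): 14.7% at p<0.01, 7.3% at 0.05, 5.8% at 0.10, 5.2% at 0.20. The 8- and 12-predictor cases give 5.2% and 5.8% at p<0.20.
- *Direction.* If half of the correlations are reversed, the error is about 5%.

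**5. The interim looks.** Assume 5% incidence and uniform accrual of 6,000/24 = 250 followed patients a month. Expected events are about 32, 76, 139, 207, 257 and 300. With 16 terms that is 32/16 = 2 events per term at the first look and 76/16 ≈ 4.8 at the second. At the final analysis it is 240/16 = 15 to 480/16 = 30.

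With 8 predictors (correlation 0.10, HR 1.10) and a nominal level of 1.42%, H1 alone rejects at 1.7%, 2.2%, 2.6%, 2.8%, 2.8% and 2.8% over the six analyses. For weak confounders the excess is thus smallest at the first look. Strong ones behave differently: four at HR 1.28 give 7.3% over six looks with reselection against 5.1% at the final test alone, so there the small excess arises early. Across the scenarios, reselection adds at most about 2 points to the final-look figure.

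**6. Cost of forcing covariates.** At HR 1.18 and 300 events, R² = 0.05, 0.10 and 0.20 (assumed) give power 0.80, 0.78 and 0.73, against 0.82.

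**The case against.** The best defence is that selection is blind to NIRS and IVUS, so covariates cannot be chosen to favour LCBI. That is correct: with no confounders the error is nominal. The excess needs several weak confounders pushing LCBI in one direction and a fairly strict entry rule, and the documents supply none of these. Section 2.1 reports only two independent clinical predictors in the earlier imaging cohort, which gives no support for 8 or 12 equal ones. Hypothesis 1 as worded in Section 6.1 is simply no association, which the univariate test addresses without adjustment. All of this stands, and it makes the size of the problem conditional.

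Four stronger readings are tempting and are not supported:
- *The covariates are reselected at every look.* Section 6.1 describes one selection; Section 6.3 neither repeats nor freezes it.
- *The problem is worst at the first look.* For weak confounders the reverse holds.
- *The H1 rejection rates are false-stop rates.* Section 6.3 also requires H2 to cross, and then the DSMB only may recommend stopping.
- *Segment type in H2 is left to screening.* It is already in every model.

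What the defence does not answer is that the entry level, the candidate list and the handling across looks are all open. The entry level alone moves the error from 5.2% to 14.7% in one scenario.

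**Conclusion.** The point holds as a gap in pre-specification with a conditional effect on error. The definitive H1 test can reject too often for the claim of incremental value. Final type I error is mostly about 7% to 12% at nominal 5% with 4 to 12 weak same-direction confounders (HR about 1.1 per SD, correlation 0.1 to 0.2) and entry at p<0.05, at 300 to 510 events. The mildest such case gives 5.7%. The error is close to 5% with no confounders, with strong ones, or with entry at p<0.20. Missed confounding is the main cause; reselection, if it happens, is secondary. A reader should not infer that the test is certainly inflated or that false early stopping is likely. Confounder strength, correlation, direction, independence of candidates, entry level and accrual are assumptions. Selection is also unnecessary at the final analysis, where 15 to 30 events per term are expected. The change is worth making because it costs little.

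**What to change.** - In 6.1, replace step-up selection with a closed list of baseline covariates, fixed in advance and all forced into the H1 model. Remove lipid levels during follow-up. Test LCBI by the Wald test in that model at the final analysis.
- In 6.3 or the SAP, fix in advance the model for each DSMB look. Use a smaller core set, or a penalised clinical score, at the early looks, where about 30 to 75 events cannot support about 16 terms. Correct the reference to Section 5.1.
- Keep step-up selection as an exploratory analysis.
- For H2, keep segment type as planned and also force in segment length, in place of screening on the outcome.

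The cost is protocol and SAP wording, plus the modest loss of power shown in step 6 of the working. The power statement in 6.2 should allow for that R².

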5.1.4 FOLLOW UP

Follow up:

The site will be notified prior to the 60 day follow up window whether or not the patient requires follow up per the algorithm listed in section 5.1.2.2, Allocation to Follow up. The NIRS Core Lab will notify the enrolling site of the follow up allocation without unblinding the max 4mm LCBI per patient value.

Patients allocated to the 24 month follow up group will undergo clinic or telephone contact or medical record review at 60 days (± 14 days), 6 months (± 14 days), 12 months (± 30 days) and 24 (± 30 days) months. The follow up will include the review for the occurrence of NC-MACE following hospital discharge from the Index Procedure or the last follow up. If the lipid profile was clinically evaluated following hospital discharge from the Index Procedure or the last follow up, these values will be recorded within the electronic case report form.

Patients will have essential data collected at the time of index enrollment. These data will be collected by an electronic data capture system.

NC-MACE Occurrence:

Once an event has been identified by the coordinator, additional source documentation regarding the event will be collected. These data will be submitted to the Clinical Event Committee for adjudication to confirm that a NC-MACE has occurred, and, if possible, to identify the site of the Follow up Culprit Lesion causing the event. Such supporting documents will include, but not be limited to:

Death certificates, autopsy reports, discharge summaries, relevant progress notes from rehospitalizations for ischemia or angina, catheterization reports, surgical reports, angiograms (films), re-imaging (films), etc.

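### Lipids measured during follow-up, possibly after the event, are candidate covariates for the NRI and, by inference, for the adjusted Hypothesis 1 model

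*Combined protocol and SAP*

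**What the plan says.** Protocol section 6.1 builds the adjusted analysis of Hypothesis 1 in steps. A step-up regression, blinded to NIRS and IVUS, picks the clinical predictors of NC-MACE. Then "When that model has been selected, max 4mm LCBI will be added to the model to assess its incremental prognostic value". Of this addition the plan says "This will be the definitive test of Hypothesis 1". The NRI is estimated from the results of the same models.

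The covariate list follows, introduced by "Other covariates to be considered as possible prognostic factors in the NRI analysis include but are not limited to". It includes total cholesterol as one item and, as another, "plasma lipid levels at baseline and during follow-up if available and history of renal insufficiency". Other items that carry a time are tied to imaging, the index catheterization or discharge. The lipid entry is the only one expressly taken from follow-up.

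On Hypothesis 2, the NRI paragraph of section 6.1 adds: "The covariates considered in the vulnerable patient analysis will again be considered in the vulnerable plaque analysis".

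Section 5.1.4 describes how follow-up lipids arise: "If the lipid profile was clinically evaluated following hospital discharge from the Index Procedure or the last follow up, these values will be recorded". There is no protocol-driven sample.

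Section 6.3 bases interim review on whether, "in the multivariate analyses described in Section 5.1, both the vulnerable patient and the vulnerable plaque null hypotheses are statistically significant" at the Pocock-adjusted level. (The reference to Section 5.1 appears to mean 6.1.)

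**The concern.** The study claims that a measurement made at imaging predicts events over the next 24 months, and that it adds to what is already known about the patient. The comparator should therefore contain only what is known at about that time. A lipid value taken during follow-up may be drawn after the NC-MACE and may have changed because of it, for instance through treatment or acute illness. Whether it exists at all depends on clinical care, which may itself depend on having had an event.

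The plan does not limit these values to those drawn before an event. It does not ask for time-dependent coding, say which draw counts, say whether baseline lipid stays in the model beside the follow-up value, or say how missing values are handled. At stake are the NRI for both hypotheses and, if the same list feeds the step-up regression, the clinical model to which LCBI is added for the definitive Hypothesis 1 test.

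**Working it through.** **1. The plan's own figure.** Section 6.2 assumes 6,000 evaluable patients, SD 100 for max 4mm LCBI and two-sided alpha 0.05. For Cox regression on a continuous covariate, power = Φ(√D × SD × ln HR − 1.96), with D the number of events and SD in units of 100. At 5% incidence D = 6,000 × 0.05 = 300, and at HR 1.18: √300 × ln 1.18 = 17.32 × 0.1655 = 2.867; 2.867 − 1.96 = 0.907; Φ = 0.818. Table 2 gives 0.82, and all 15 cells reproduce to rounding. The formula contains no other covariates, so Table 2 does not depend on this point.

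**2. Assumptions for the illustration.** The documents give no lipid figures. The base is 6,000 patients, about 300 events and exponential times censored at 24 months. Assumed for items 4 and 5: lipid HR 1.2 per SD, baseline/follow-up lipid correlation 0.7, LCBI/baseline-lipid correlation r of 0.2 or 0.4 (0 to 0.4 for the NRI), and follow-up lipid lowered by 0.3 or 0.5 SD after an event.

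**3. Selection.** Give lipids no true effect, make them independent of LCBI, and lower the follow-up value by 0.25, 0.5 or 1.0 SD after events. Entered as a fixed covariate, it is significant at 0.05 in 98%, 100% and 100% of 200 runs. Baseline lipid is significant in 2-7%. A step-up procedure would readily pick the shifted value.

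**4. NRI, both lipids in the clinical model.** Assumed 5% risk cut, unweighted, true LCBI odds ratio 1.18, r from 0 to 0.4, every event patient shifted:

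| Clinical model | AUC | NRI at 5% cut |
|---|---|---|
| Baseline lipid only | 0.549-0.570 | 0.018-0.027 |
| Plus follow-up lipid, no shift | 0.553-0.571 | 0.018-0.025 |
| Plus follow-up lipid, 0.3 SD shift | 0.626-0.636 | 0.007-0.012 |
| Plus follow-up lipid, 0.5 SD shift | 0.695-0.700 | 0.006-0.009 |

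The category-free NRI stays at 0.12-0.13 throughout. The plan does not say which form it will use.

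**5. Adjusted LCBI hazard ratio when the true value is 1.00.**

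| Lipid terms in the model | Event patients shifted | LCBI HR |
|---|---|---|
| Baseline and follow-up | all | 0.99-1.015 |
| Follow-up only | all | 1.06-1.09 (r 0.2); 1.14-1.21 (r 0.4) |
| One merged variable (follow-up if tested, else baseline) | all | 1.04-1.09 (r 0.2); 1.08-1.19 (r 0.4) |
| Follow-up plus baseline total cholesterol (assumed correlation 0.9 with baseline lipid) | all | about 1.02-1.08 |
| Follow-up only | half | about 1.03-1.12 |
| Follow-up plus baseline total cholesterol | half | about 1.00-1.04 |

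At r = 0 there is no bias in any model. With no shift, follow-up lipid alone gives 1.02-1.05, which is residual confounding and not a post-event effect. With complete lipids, a step-up at p<0.05 (assumed) kept both lipids in every shifted run, which is the first row.

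**6. Availability.** If lipids exist for 80% of event and 50% of non-event patients (assumed), a complete-case model keeps 0.8 × 300 = 240 events and 0.5 × 5,700 = 2,850 others, 3,090 in all. The event fraction rises from 5% to 240/3,090 = 7.8%.

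**The case against.** **The list is worded for the NRI.** It follows the sentence on the definitive test, and its items are only to be considered. This stands: use in the Hypothesis 1 model is an inference. It is a reasonable one, because the NRI comes from those models and no other candidate list is given.

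**A reader might infer that the plan builds a large bias into the Hypothesis 1 hazard ratio.** The documents do not support that. The entry names baseline and follow-up lipids together, and with both in the model the bias is essentially nil. Total cholesterol is a separate candidate, so losing all baseline lipid information is less likely; its date is not stated, and the figures above read it as baseline. Shifting every event patient is also extreme: the composite includes cardiac death, after which there is no lipid test, and some event patients will have only pre-event values.

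**A reader might also infer that the bias could stop the study early.** Section 6.3 requires both null hypotheses to be rejected before the DSMB may recommend termination, and the Hypothesis 2 test model is described through segment characteristics. Bias in Hypothesis 1 alone could not trigger the recommendation.

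**Rejection rates at 1.96 are not this study's error rates.** With follow-up lipid alone and every event patient shifted, 18-31% (r 0.2) and 56-87% (r 0.4) of null runs exceed 1.96. Section 6.3 sets a Pocock level. At an assumed 2.45 (five interim reviews plus the final, equally spaced) the rates are 9-13% and 40-77%, against a nominal 1.4% or so. They are still inflated, but only in that unfavourable case.

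**Any shrinkage of the NRI works against the device.** True, and the illustration is unweighted although section 6.1 requires weighting. A conservative error is still an error in a stated measure of performance.

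**Conclusion.** The point holds as a gap in covariate timing. The plan expressly admits lipid values from follow-up, selectively measured and possibly drawn after the event, into the NRI comparator for Hypothesis 1. It carries the covariates to the Hypothesis 2 NRI and, by inference, lets them into the step-up model behind the definitive Hypothesis 1 test.

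The main consequence is that a post-event lipid shift is easily taken for a predictor, makes the clinical model look too good and can shrink a category-based NRI, by roughly half or more under the stated assumptions. Bias in the adjusted LCBI hazard ratio is conditional: baseline lipid information must be dropped or merged with follow-up values, and LCBI must correlate with lipids. The more moderate case, with half of event patients shifted, gives a null hazard ratio of about 1.03-1.12, or about 1.00-1.04 if baseline total cholesterol stays in. Correlation, shift and availability are all assumed; with no shift this source adds no material bias.

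The univariate Wald test, Table 2 and the Hypothesis 2 test model as described are unaffected. This is a free improvement, not a flaw that invalidates the primary test.

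**What to change.** In the lipid entry of the section 6.1 covariate list, keep the baseline values and strike the five words that add follow-up values. Then add:

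*Candidate covariates for the Hypothesis 1 multivariate model and for the Hypothesis 1 and Hypothesis 2 NRI are limited to values determined by discharge from the index hospitalisation and before any NC-MACE. Follow-up lipids are summarised descriptively, or used only in a separate exploratory time-updated model in which a value counts from its measurement date and no value drawn on or after the first NC-MACE is used.*

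The condition about NC-MACE is needed because the schedule of contacts records MACE from the index visit, so a discharge limit alone could admit a value taken after an in-hospital event. The rule also fixes the timing of total cholesterol, which is now undated.

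The cost is one phrase removed and two sentences added. Data collection and the sample size are unchanged, and follow-up lipids stay available for description.
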